4.10 Automated Closed loop System (FlorenceM) to be used in the Present Study

The automated closed loop system (FlorenceM) will consist of:

- Next generation sensor augmented Medtronic insulin pump 640G (Medtronic Minimed, CA, USA) incorporating the Medtronic Enlite 3 family real time CGM and glucose suspend feature.
- An Android smartphone containing the Cambridge model predictive algorithm and communicating wirelessly with the insulin pump using a proprietary translator device.

An overview of this proposed automated closed loop system is given in Figure 1.

Figure 1: Representative design of the proposed FlorenceM automated closed loop system

4.11 Rationale for the Current Study

No study thus far has combined the pump suspend feature with closed loop insulin delivery. During our previous closed loop studies, if there is a communication failure between the algorithm device and the insulin pump, the pump is set to deliver pre-programmed basal insulin rates after about 30 to 60 minutes. Adding the pump suspend feature to closed loop will further increase patient safety by stopping the pump at low glucose levels even if there is a communication failure between control algorithm device and the insulin pump. In addition the current study will provide further evidence on the effect of consecutive closed loop day and nights over multiple weeks in a relatively large group of adults and children with type 1 diabetes in a multi-centre and multi-national setting to demonstrate the generalisability of results.

5 Objectives

5.1 Efficacy

The objective is to assess efficacy of day and night automated closed loop glucose control combined with pump suspend feature in maintaining glucose levels within the target range from 3.9 to 10.0mmol/l based on subcutaneous continuous glucose monitoring (CGM), as compared with sensor augmented insulin pump therapy alone.

5.2 Safety

The objective is to evaluate the safety of day and night automated closed loop glucose control combined with pump suspend feature in terms of episodes of severe hypoglycaemia and other adverse events.

5.3 Utility

The objective is to determine the frequency and duration of use of the automated closed loop system.

5.4 Psychosocial

Subjects' and family members' perception in terms of life-style change, diabetes management will be assessed using validated questionnaires and semi-structured qualitative interviews.

6 Study Design

An open-label, multi-centre, multi-national, randomised, single-period parallel study, in youth (6 to 21 years) and adults (22 years and older) with type 1 diabetes on insulin pump treatment will contrast day and night automated closed loop glucose control combined with pump suspend feature with sensor augmented insulin pump therapy alone.

It is expected that up to 100 youths and adults with type 1 diabetes with T1D will be recruited, aiming for 84 randomised subjects. Subjects who drop out within the first four weeks of the intervention may be replaced. Subjects who dropout prior to the final visit will receive an exit survey. The study flow chart is outlined in Figure 2.

7 Study Subjects

7.1 Study Population

[figure not shown]
This is a multicentre and multinational study and recruitment will take place at the following centres:

1. Addenbrooke's Hospital, Cambridge, UK (adults and youth)
2. Royal Hospital for Sick Children, Edinburgh, UK (youth)
3. Leeds Teaching Hospital, Leeds, UK (youth)
4. Manchester Royal Infirmary, Manchester, UK (adults)
5. International Diabetes Center at Park Nicollet, Minneapolis, USA (adults and youth)
6. Barbara Davis Center for Childhood Diabetes, Aurora, USA (adults)

Up to a total of 50 youths aged 6 to 21 years and 50 adults aged 22 years and older with type 1 diabetes on insulin pump therapy will be recruited. Each centre will aim to recruit between 10 to 20 participants but may recruit more if needed

Potential participants will be identified by their treating clinicians and invited to contact the research team. They will be sent the study information leaflets and an invitation to join the study by the research team at least one day before the recruitment visit.

Figure 2. Study flow chart

7.2 Inclusion Criteria

1. The subject is at least 6 years or older [with equal proportion of youth (6 to 21 years) and adults (22 years and older)]
2. The subject has type 1 diabetes, as defined by WHO for at least 1 year or is confirmed C-peptide negative
3. The subject will have been an insulin pump user for at least 3 months, with good knowledge of insulin self-adjustment as judged by the investigator
4. The subject is treated with one of the U-100 rapid acting insulin analogues only (insulin Aspart, Lispro but not Glulisine)
5. The subject/carer is willing to perform regular capillary blood glucose monitoring, with at least 4 blood glucose measurements taken every day
6. Screening HbA1c $\geq 7.5\%$ (58.5mmol/mol) and $\leq 10\%$ (86mmol/mol) based on analysis from local laboratory or equivalent [with equal proportion of subjects above and below HbA1c 8.5% (69mmol/mol)]
7. The subject is literate in English
8. The subject is willing to wear glucose sensor
9. The subject is willing to wear closed loop system at home
10. The subject is willing to follow study specific instructions
11. The subject is willing to upload pump and CGM data at regular intervals
12. The subject is willing to restrict alcohol consumption to ≤ 2 units per day throughout the study period
13. Female subjects of child bearing age should be on effective contraception and must have a negative urine-HCG pregnancy test at screening.
14. The subject lives with someone who is trained to administer intramuscular glucagon and is able to seek emergency assistance.
15. The subject has access to WiFi at home.

7.3 Exclusion Criteria

1. Non-type 1 diabetes mellitus including those secondary to chronic disease
2. Subject using real-time CGM on regular basis in preceding 3 months
3. Any other physical or psychological disease likely to interfere with the normal conduct of the study and interpretation of the study results as judged by the investigator
4. Untreated coeliac disease, adrenal insufficiency, or hypothyroidism
5. Current treatment with drugs known to interfere with glucose metabolism, e.g. systemic corticosteroids, non-selective beta-blockers and MAO inhibitors etc.
6. Known or suspected allergy to insulin

7. Clinically significant nephropathy (eGFR < 45ml/min) or on dialysis, neuropathy or active retinopathy (defined as presence of maculopathy or proliferative changes) as judged by the investigator
8. Adults: one or more episodes of severe hypoglycaemia as defined by American Diabetes Association (33) in preceding 6 months; Youth: one or more episodes of severe hypoglycaemia during the previous 6 months (Adults and adolescents: severe hypoglycaemia is defined as an event requiring assistance of another person to actively administer carbohydrates, glucagon, or take other corrective actions including episodes of hypoglycaemia severe enough to cause unconsciousness, seizures or attendance at hospital; children: severe hypoglycaemia is defined as an event associated with a seizure or loss of consciousness);
9. Random C-peptide > 100pmol/l with concomitant blood glucose >4 mmol/l (72 mg/dl)
10. Regular use of acetaminophen
11. Lack of reliable telephone facility for contact
12. Total daily insulin dose \geq 2 IU/kg/day
13. Total daily insulin dose < 15 IU/day
14. Pregnancy, planned pregnancy, or breast feeding
15. Severe visual impairment
16. Severe hearing impairment
17. Significantly reduced hypoglycaemia awareness in subjects 18 year and older (screening Gold score > 4)
18. Subjects using implanted internal pace-maker
19. Patients with medically documented allergy towards the adhesive (glue) of plasters or Subject is unable to tolerate tape adhesive in the area of sensor placement
20. Serious skin diseases (e.g. psoriasis vulgaris, bacterial skin diseases) located at places of the body, which potentially are possible to be used for localisation of the glucose sensor)
21. Subject is currently abusing illicit drugs
22. Subject is currently abusing prescription drugs
23. Subject is currently abusing alcohol
24. Subject is using pramlintide (Symlin) or other commonly used hypoglycaemic agents including sulphonylureas, biguanides, DPP4-inhibitors, GLP-1 agonists, SGLT-2 inhibitors at time of screening
25. Subject has elective surgery planned that requires general anaesthesia during the course of the study
26. Subject is a shift worker with working hours between 10pm and 8am
27. Subject has a sickle cell disease, haemoglobinopathy; or has received red blood cell transfusion or erythropoietin within 3 months prior to time of screening

28. Subject plans to receive red blood cell transfusion or erythropoietin over the course of study participation
29. Subject diagnosed with current eating disorder such as anorexia or bulimia
30. Subject plans to use significant quantity of herbal preparations (use of over the counter herbal preparation for 30 consecutive days or longer period during the study) or significant quantity of vitamin supplements (four times the recommended daily allowance used for 30 consecutive days or longer period during the study) known to affect glucose metabolism and/or blood glucose levels during the course of their participation in the study

7.4 Randomisation

Eligible subjects will be randomised using central randomisation software to the use of day and night closed loop combined with pump suspend feature or to sensor augmented insulin pump therapy. The randomisation will be stratified at each centre by HbA1c groups [equal proportion of below and above 8.5% (69mmol/mol)]. Each site will recruit only in one of the two age groups [youth (6 to 21 years) or adults (22 years and older)].

8 Methods under Investigation

8.1 Name and Description of the Method of Investigation

The investigational treatment is the FlorenceM, see section 4.10, or follow up prototypes of the automated day and night closed loop system manufactured by the Cambridge University Hospitals NHS Foundation Trust and supported by Medtronic Minimed Inc. Northridge, CA, USA. Component versions will be identified during regulatory submission to the MHRA / FDA.

8.2 Intended Purpose

The intended purpose of the investigational treatment is automated day and night closed loop insulin delivery combined with pump suspend feature.

8.3 Method of Administration

The closed loop system consists of components directly attached to the patient, which are the CGM transmitter and the insulin pump. The component not directly attached to the patient is the handheld smartphone containing closed loop algorithm and communicating wirelessly with the insulin pump.

8.4 Required Training

Prior to commencement of the study, the research team nurses/clinicians at each of the investigation centres will be trained to use the closed loop system and its components. Prior to the use of study devices, participants will be trained to use the study CGM device, the study pump and where appropriate the closed loop system. Competency assessments of the participants' capability to use study devices and the closed loop system will be made.

8.5 Precautions

During treatment with insulin there is a risk of hypoglycaemia and hyperglycaemia. In-hospital testing and Hazard Analysis both documented reduced risk of hypoglycaemia and hyperglycaemia during day and night closed loop compared to conventional treatment. Addition of pump suspend feature will further increase safety.

8.6 Accountability of the Method under Investigation

The local Investigator will provide training for the study participants and will make every effort, through regular contact, to ascertain that the closed loop system is used for the study purposes only. Devices will be identified using batch/lot/serial numbers and the location of investigational devices and their dates of use by subjects will be documented throughout the study.

9 Study Schedule

9.1 Overview

The study will be co-ordinated from the Institute of Metabolic Science, Addenbrooke's Hospital, Cambridge, and performed at following sites:

1. Addenbrooke's Hospital, Cambridge, UK
2. Royal Hospital for Sick Children, Edinburgh, UK
3. Leeds Teaching Hospital, Leeds, UK
4. Manchester Royal Infirmary, Manchester, UK
5. International Diabetes Center at Park Nicollet, Minneapolis, USA
6. Barbara Davis Center for Childhood Diabetes, Aurora, USA

After recruitment, consent, and run-in period, subjects will be randomised for three months home use of real-time CGM combined with automated day and night closed loop insulin delivery or three months during which they will use sensor augmented pump therapy alone.

The study includes up to 11 visits and 6 telephone/email contacts for subjects completing the study. The visit to set up automated closed loop for the first time may take place in the home setting or alternatively in an in-patient facility. All other visits can take place at the hospital clinic, home or other suitable meeting place, according to participants' convenience. Maximum time in study is 18 weeks.

Table 1 outlines study activities when participant is randomised to day and night closed loop (intervention group).

Table 2 outlines study activities when participant is randomised to sensor augmented pump therapy alone (control group).

Table 1. Schedule of study visits / phone contacts when the participant is randomised to day and night closed loop combined with pump suspend feature (intervention group).

	Visit/ contact	Description	Start relative to previous / next Visit / Activity	Duration
	Visit 1	Recruitment visit: Consent, HbA1c, screening bloods & questionnaires, urine pregnancy test	-	1-4 hours
Training & Run-in (4 wks)	Visit 2	Insulin pump training and the initiation study pump Competency assessment	Within 1 to 3 weeks of Visit 1	3-4 hours
	Visit 3	CGM training Initiation of CGM Weekly contact via phone/email Competency assessment	Within 3 to 7 days of Visit 2	2-3 hours
	*Visit 4	Review pump and CGM data & optimisation of treatment & compliance assessment & randomisation	After 4 weeks of Visit 3	<1 hour
	Contact	Qualitative interview (with a subset of participants/family members)	After randomisation but before Visit 5	<1 hour
CL + LGS Intervention (3 months)	Visit 5	CL initiation at clinic/home - urine pregnancy test - CL and suspend feature training - competency assessment - HbA1c	Within 1 week of Visit 3	2-6 hours
	* Visit 6	Review use of study devices	After 24-48 hours of Visit 5	<1 hour
	**Visit 7	Review use of study devices	After 1 week of Visit 5	<1 hour
	*Visit 8	Review pump and CGM data	After 1 week of Visit 7	<1 hour
	*Visit 9	End of first month: Review pump and CGM data	After 2 weeks of Visit 8	<1 hour
	*Visit 10	End of second month: Review pump and CGM data	After 4 weeks of Visit 9	<1 hour
	Visit 11	End of closed loop treatment arm (3 months): HbA1c, Complete questionnaires, and follow-up qualitative interviews	After 4 weeks of Visit 10	1-3 hours

*Could be done via phone / e-mail in UK. Follow-up by phone is mandatory in US only.

** Could be done via phone / e-mail in UK. In-person visit mandatory in US only.

Table 2. Schedule of study visits / phone contacts when the participant is randomised to sensor augmented pump.

	Visit/ contact	Description	Start relative to previous / next Visit / Activity	Duration
	Visit 1	Recruitment visit: Consent HbA1c, screening bloods & questionnaires, , urine pregnancy test	-	1-4 hours
Training & Run-in (4 wks)	Visit 2	Insulin pump training and the initiation study pump Competency assessment	Within 1 to 3 weeks of Visit 1	3-4 hours
	Visit 3	CGM training Initiation of CGM Weekly contact via phone/email Competency assessment	Within 3 to 7 days of Visit 2	2-3 hours
	*Visit 4	Review pump and CGM data & optimisation of treatment & compliance assessment & randomisation	After 4 weeks of Visit 3	<1 hour
SAP Intervention (3 months)	Visit 5	SAP initiation at clinic/home - urine pregnancy test - SAP training - competency assessment - HbA1c	Within 1 week of Visit 4	2-6 hours
	*Visit 6	Review use of study devices	After 24-48 hours of Visit 5	<1 hour
	**Visit 7	Review use of study devices	After 1 week of Visit 5	<1 hour
	*Visit 8	Review pump and CGM data	After 1 week of Visit 7	<1 hour
	*Visit 9	End of first month: Review pump and CGM data	After 2 weeks of Visit 8	<1 hour
	*Visit 10	End of second month: Review pump and CGM data	After 4 weeks of Visit 9	<1 hour
	Visit 11	End of SAP treatment arm (3 months): HbA1c, Complete questionnaires.	After 4 weeks of Visit 10	1-3 hours

*Could be done via phone / e-mail in UK. Follow-up by phone is mandatory in US only.

** Could be done via phone / e-mail in UK. In-person visit mandatory in US only.

9.2 Recruitment Visit and Screening Assessment (Visit 1)

Once the subjects have agreed to participate in the study, they will be invited for the recruitment visit, when the following activities will be performed by the research team:

- written informed consent/assent
- checking inclusion and exclusion criteria
- medical (diabetes) history
- body weight and height measurement; calculation of BMI
- record of current insulin therapy
- urine pregnancy test (females of child-bearing potential)
- record of occupation and educational attainment

9.2.1 Screening Blood Sampling

Blood samples will be taken for the screening measurement of random C-peptide, glucose, and HbA1c (measured at a local laboratory). Liver, renal, thyroid function, full blood count, anti-transglutaminase antibodies and IgA will also be evaluated (if not done in previous 3 months). Less than 15 ml of whole blood will be taken from each participant.

9.2.2 Questionnaires at Screening

Validated questionnaires will be distributed to assess quality of life before entering the study.

9.3 Training Session on the use of the Study Insulin Pump (Visit 2)

This session will cover key aspects of insulin pump use and particular attention will be paid to the following areas:

- Importance of carbohydrate counting and refresher on carbohydrate counting skills
- Understanding insulin to carb ratios and correction factors
- Correct use of bolus calculator - subjects will be required to use this bolus calculator for all insulin boluses during the study period.
- Insulin cartridge and Infusion set changes and correct priming procedure
- Sick day rules
- Dealing with hypo and hyperglycaemia
- Uploading pump data

Written easy to use guidelines for the operation of insulin pump will be provided.

UK only

This session will be conducted by a professional pump educator ± member of the study team following a written curriculum. Competency on the use of study pump will be made.

US only

This session will be conducted by a professional pump educator ± member of the study team with the subject (accompanied by a caregiver/guardian if <18years of age) following a written curriculum. Competency on the use of study pump by the subject (and caregiver/guardian if <18years of age) will be made.

9.4 Training Session on Continuous Glucose Monitoring (Visit 3)

This session will cover key aspects of the study CGM and particular attention will be paid to the following areas:

- Insertion and initiation of sensor session
- Using sensor menu of the insulin pump & sensor calibrations
- Use of software to analyse CGM data
- Use of CGM data to optimise treatment
- Uploading CGM data using Carelink or similar software

Written guidelines for the operation and use of CGM device will be provided.

UK only

This session will be conducted by a professional pump educator and possibly a member of the study team. Competency on the use of CGM will be made.

US only

This session will be conducted by a professional pump educator and possibly a member of the study team with the subject (accompanied by a caregiver/guardian if <18years of age). Competency on the use of CGM by the subject (and caregiver/guardian if <18years of age) will be made.

9.5 Run-in Period (ends at Visit 4)

The subject will use study insulin pump and study CGM over the run-in period. The subject will be invited to attend the research centre or contacted via e-mail / telephone at the end of the run-in period. Study insulin pump and CGM device will be downloaded and data may be used for treatment optimisations. There should be a minimum of four weeks run-in period for all subjects (end of Visit 3 to end of Visit 4). Subjects will be contacted once weekly during the run-in period via phone/email to troubleshoot any problems. Subjects will also be able to contact the research team in between these weekly contacts for support or to provide any additional training on the devices as required.

9.5.1 Compliance Assessment

During Visit 4, participant's compliance of using the study CGM and study pump over preceding 14 days will be assessed. To proceed with the study subject needs to demonstrate correct use of study insulin pump including use of bolus calculator over 75% of meal boluses and at least 12 days' worth of CGM data during last 14 days of run-in period. In addition, subject should carry out upload of CGM and pump data at weekly intervals. If subject fails to demonstrate compliance, the study will be terminated and subject will be removed from the study.

Subject randomisation for the treatment intervention will take place during the week following Visit 4. Maximum period allowed between Visit 3 and Visits 5 is six weeks with a minimum of four weeks.

9.6 Randomisation

Eligible subjects who have gained confidence in the use of the study insulin pump and the study CGM system, as assessed by the research team, will be randomised centrally using a randomisation based on a computer-generated random code. Randomisation will take place centrally, with an independent person being responsible for the randomisation sequence. Subjects will be allocated to one of the two intervention arms: three months use of day and night closed loop combined with pump suspend feature or three months use of sensor augmented insulin pump therapy without pump suspend feature.

9.7 Baseline Qualitative Interview

A subset of subjects/guardians randomised to the use of day and night closed loop with pump suspend feature will be invited for a qualitative interview (face to face or telephone interview) at a mutually convenient time, see section 12.2.2. Whenever possible, the interview will occur before Visit 8.

9.8 Visit 5 (Initiation of Study Treatment; within 1 Week of Visit 4 and at least 4 Weeks after Visit 3)

Subject will arrive at the clinical facility at the agreed time. Urine pregnancy test will be performed on arrival for all females of child bearing age and all subjects will have a blood test for HbA1c. Body weight measurement will be made. Subjects will be provided with necessary training on use of study devices according to randomisation. Competency assessment will be made. During the three months home treatment period, the subject will be asked to upload the study insulin pump and CGM at weekly intervals.

During the three months home closed loop treatment, the subject is allowed to drive while adhering to usual precautions and country specific rules and regulations.

During the first 2 weeks of each study period subject will be advised against international travel. During the rest of the study period, participants are allowed to travel internationally according to guidelines provided in the participant information sheet.

Subjects will be provided with 24 hour telephone helpline and will also be given written instructions about dealing with low and high glucose at home and when to contact study team. It is also possible to conduct Visit 8 in subject's home.

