9.11 Visit 8 – 2 Weeks after Starting Study Treatment

The subject will either be contacted via telephone/e-mail or seen in the clinic 1 week after Visit 7. The purpose of this visit would be to troubleshoot any problems. The subject is free to optimise further treatment but no active treatment optimisation will be undertaken by the study team.

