12.2.2 Qualitative Interview

A subset of participants randomized to a closed loop system will be interviewed at baseline (post-randomization) to enable their historical diabetes management practices, everyday work and family lives, and their initial expectations of using this technology to be captured and explored in-depth. The same participants will be followed-up 3 months later to look at whether, in what ways, and why, use of a closed loop system has impacted on their diabetes self-management practices, their attitudes towards hypoglycaemia; and, their work and family lives. These follow-up interviews will also explore how participants think the technology could be refined and improved in light of their

experiences of using it. A subset of family members will be interviewed at 3 months to capture the benefits of using a closed loop system from their perspectives, including how this technology has impacted on their own lives and on their role in supporting diabetes management practices. A family member recruitment pack will be given to participants/guardians at Visit 8 to pass onto a partner/adult family member in order to recruit the subset of family members for the interviews at 3 months. The family member recruitment pack can also be mailed or emailed after Visit 8 to participants/guardians.

Approximately 25 people with diabetes will be interviewed. This sample size will be large enough for a full range of issues relating to use of closed loop systems to be identified and explored in-depth and for data saturation to occur (i.e. for no new findings to emerge from any new data collected). If possible, participants will be purposively sampled so there is diversity in the final sample in terms of age, gender, occupation/education and geographical location. Approximately 20 family members will be interviewed.

Interviews will be informed by topic guides developed in light of literature reviews, initial research questions, inputs from the trial team and lay/patient advisors, and revised in light of emerging findings (see above). UK based interviews will take place at a time and location chosen by participants (most likely their own homes) and possibly by phone; US interviews will need to be undertaken by telephone. Interviews will be digitally recorded with consent and will average an hour.

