To maximise rigour two experienced qualitative researchers will be involved in data analysis. A thematic analysis will be undertaken by these two individuals who will independently review all data before attending regular meetings to compare their interpretations and reach agreement on recurrent themes and findings. Each individual's baseline and three month interview will be compared, and attention paid to any continuities and changes in their attitudes, experiences and use of closed loop systems over time, and the reasons for these. Participants' accounts will also be cross-compared, enabling the identification of overarching themes which cut across different people's experiences. A final coding frame, reflecting the initial research questions and emergent themes, will be developed once all data have been reviewed and consensus reached on key themes and findings. NVivo9, a qualitative software package, will be used to facilitate data coding/retrieval.

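### Section 9.7 ties the baseline interview to Visit 8, after closed loop has begun, while Table 1 requires it before Visit 5; the two need reconciling

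*Protocol*

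**What the plan says.** Four parts of the Protocol bear on when the baseline interview takes place and what it is for.

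- **Section 9.7 (Baseline Qualitative Interview):** a subset of those randomised to closed loop is invited to interview, and "Whenever possible, the interview will occur before Visit 8".
- **Section 9.1, Table 1:** the row for the qualitative interview sits between Visits 4 and 5 and gives its timing as "After randomisation but before Visit 5".
- **Heading of section 9.8:** "Visit 5 (Initiation of Study Treatment; within 1 Week of Visit 4 and at least 4 Weeks after Visit 3". Visit 5 is therefore the first day of closed-loop use for the intervention arm.
- **Section 12.2.2 (Qualitative Interview):** the baseline interview, described as post-randomisation, is to allow participants' past management practices, their daily lives and "their initial expectations of using this technology to be captured and explored in-depth". In the analysis, "Each individual's baseline and three month interview will be compared".

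The synopsis row for the intervention arm also describes the interview ahead of the Day 1 admission and training.

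**The concern.** The two timing instructions cannot both govern. Under Table 1 no participant has used closed loop when interviewed. Under section 9.7 a participant may have used it for two weeks, and the qualifier in that sentence makes even Visit 8 a target rather than a limit.

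What is at stake is the part of the interview that depends on timing. Expectations of a device can be recorded prospectively only before it is used. Afterwards they are recollections coloured by experience, and early changes in self-management may already be in the account that serves as the baseline. Section 12.2.2 then sets that account against the three-month interview to describe continuity and change. An interview missed before first use cannot be recovered later.

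**Working it through.** No sample-size, power or error-rate calculation is involved. The check is visit arithmetic plus a side-by-side reading.

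**Inputs**
- Start of closed loop: Visit 5, taken as day 0 (heading of section 9.8).
- Visit 7: "After 1 week of Visit 5" (Table 1).
- Visit 8: "After 1 week of Visit 7" (Table 1).
- Length of the intervention: 84 days (section 14.6; 12 weeks × 7).
- Use in between: section 9.8.1 expects closed loop to be used continuously throughout the intervention.

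**The Protocol's own figure**
- Visit 8 = Visit 5 + 7 days + 7 days = day 14. This agrees with the heading of section 9.11, which places Visit 8 "2 Weeks after Starting Study Treatment".

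**Closed-loop exposure possible before the baseline interview**

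| Instruction followed | Latest time | Exposure allowed |
|---|---|---|
| Table 1 | before Visit 5 | 0 days |
| Section 9.7 | before Visit 8, where possible | up to about 14 days; longer if the qualifier is used |

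- Share of the intervention: 14 / 84 = 16.7%, about one sixth.

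**Is Visit 8 a numbering slip?** Two other places suggest so.
- Section 9.8, which describes Visit 5, ends by saying that Visit 8 may be held at the participant's home. That fits section 9.1, where the closed-loop set-up visit may be at home, only if Visit 5 is meant.
- Table 1 counts the one-week window for Visit 5 from Visit 3, while Table 2 and section 9.8 count it from Visit 4.

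Visit 8 is nevertheless a real, defined visit. Section 12.2.2 refers to it without apparent error, for handing out the family-member recruitment pack. Nothing in section 9.7 tells a reader that the number is wrong.

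**Room for the Table 1 timing.** Section 9.5.1 places randomisation in the week after Visit 4, and section 9.8 places Visit 5 within one week of Visit 4. The interval from randomisation to Visit 5 is therefore at most about a week and may be only days.

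**The case against.** The strongest reply is that this is an editorial slip and not a plan to interview after exposure. Table 1 and the synopsis both put the interview first, and the stray Visit 8 in section 9.8 points to old numbering. That explanation is probably right. It does not remove the conflict, because section 9.7 is the operative text on this interview and someone following it literally would be complying with the Protocol.

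A second reply is that section 12.2.2 defines baseline only as post-randomisation. That fixes the earliest time and leaves the latest to Table 1, which section 9.7 contradicts. It is fair, though, that past practices and daily life can still be described after some use, so a late interview is not worthless. Only the account of expectations is clearly sensitive to timing. The qualifier may also be a deliberate allowance for the short interval before Visit 5.

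A reader might infer three stronger things that the Protocol does not support:

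- **That the psychosocial objective depends on this comparison.** Sections 5.4 and 12.2.1 describe a mixed approach that includes validated questionnaires at screening and at the end of the intervention. Section 14.7 compares PedsQL scores between arms, adjusted for baseline score. Section 9.7 does not touch that part.
- **That late interviews would bias a measured effect.** Section 12.2.2 plans a thematic analysis and no change score, so there is no numerical estimate to shrink.
- **That all of the roughly 25 interviewees would have 14 days of exposure.** That is the worst case allowed by one sentence, and only if Table 1 is ignored throughout. The Protocol gives no basis for forecasting how many interviews would be late.

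**Conclusion.** The inconsistency is real and its severity is low. Section 9.7 allows about two weeks or more of closed-loop use before an interview that Table 1 requires before any use. The timing in Table 1 is the one that serves the purpose stated in section 12.2.2.

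The effect is limited to the account of initial expectations, and its comparison with the three-month interview, among about 25 closed-loop participants. The questionnaires, the primary endpoint, the randomised comparisons, the sample size and the type I error rate are unaffected.

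This rests on two assumptions: that participants use closed loop from Visit 5 as section 9.8.1 expects, and that some interviews would be scheduled from section 9.7 and not from Table 1. The numbering slip is an inference from the surrounding text and is not needed for the conclusion.

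**What to change.** In section 9.7, replace the reference to Visit 8 so that the interview takes place *after randomisation and before Visit 5*, matching Table 1. Add one clause: if an interview falls after Visit 5, its date is recorded and its account of expectations is not treated as pre-use. There is no need to exclude the whole interview from the within-person comparison, since its other content may still be usable.

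The cost is one amended sentence and a short clause. The practical downside is the short interval between randomisation and Visit 5, for interviews that section 12.2.2 expects to average an hour. Some candidates may need a telephone interview, which section 9.7 already allows, or may have to be replaced by others in the purposive sample.
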